8.3.15.4. Pregnancy Testing

A serum pregnancy test will be administered to all female New Subjects at screening. Results must be negative for a female subject to be eligible for the study.

A urine pregnancy test will be administered to all participating female subjects predose, on the first day of dosing. Results must be negative prior to administration of study drug.

At all other time point(s) specified in [Table 2](#) and [Table 3](#), all female subjects will have urine pregnancy testing; results must be negative for a subject to continue in the study.

A positive pregnancy test result at any time will necessitate the subject's immediate withdrawal from the study. Additional follow-up may be required as detailed in [Section 8.4.1](#).

8.3.15.5. Hematology, Biochemistry, and Urinalysis

Blood and urine samples for laboratory safety assessments will be collected at the time points specified in [Table 2](#) and [Table 3](#). Specific hematology, biochemistry, and urinalysis assessments are listed in [Table 4](#).

Table 4: Clinical Laboratory Assessments

Hematology	Biochemistry	Urinalysis

 • Glycosylated hemoglobin (HbA1c)^a • Hematocrit • Hemoglobin • Platelets • Red blood cell count • Total and differential (absolute) white blood cell count 	
 • Alanine transferase (ALT) • Albumin • Alkaline phosphatase (ALK-P) • Aspartate transferase (AST) • Bicarbonate • Blood urea nitrogen (BUN) • Calcium • Chlorine • Creatine phosphokinase (CPK) • Creatinine • Gamma-glutamyl transferase (GGT) • High-density lipoprotein (HDL) • Lactic dehydrogenase (LDH) • Low-density lipoprotein (LDL) • Magnesium • Phosphorus • Potassium • Prolactin^b • Random Glucose • Sodium • Thyroid-stimulating hormone^c • Total bilirubin • Total cholesterol • Total protein • Triglycerides • Uric acid 	
 • Bilirubin • Color and appearance • Glucose • Ketones • Leukocytes • Microscopic examination of sediment, only if urinalysis dipstick results are abnormal • Nitrite • Occult blood • pH • Protein • Specific gravity • Urobilinogen

^a HbA1c to be analyzed at Visits 2, 8, 10, 12, and 14/ET

^b Prolactin to be analyzed at Visits 1, 2, 10, and 14/ET

^c Only at Visit 1

Reference ranges for evaluated laboratory tests will be supplied by the assigned laboratory before the study starts. Procedures for sampling and processing laboratory assessments will be described in a separate laboratory manual.

In the event of a difficult blood draw or where there is a limited quantity of blood available for testing, blood collection for biochemistry should be prioritized over hematology.

If unexplained abnormal laboratory test values are observed, follow-up samples may be obtained for repeat testing as clinically indicated.

Results of clinical laboratory testing will appear on electronically produced laboratory reports submitted directly to the site from the central laboratory, if applicable.

8.3.16. Structured Interviews and Questionnaires

Brief descriptions of each of the structured interviews and questionnaires to be administered are provided below. [Table 2](#) and [Table 3](#) provide details on the time points during which each measure should be administered. All structured interviews and questionnaires will be administered by trained and qualified study personnel.

At screening, the medical and psychiatric history and MINI diagnostic interview must be conducted prior to the HAM-D and MADRS.

The MADRS should be administered prior to the HAM-D, CGI-S and HAM-A on visits when multiple assessments are scheduled.

8.3.16.1. Assessments for Study Eligibility

8.3.16.1.1. Massachusetts General Hospital Antidepressant Treatment Response Questionnaire

The ATRQ is a clinician-administered scale used to document history of antidepressant treatment and to determine treatment resistance in MDD. A sample of the ATRQ can be found in [Appendix C](#).

8.3.16.1.2. Mini International Neuropsychiatric Interview

The MINI is a short, clinician-administered, structured diagnostic interview, with an administration time of approximately 15 minutes. The MINI has been validated against the much longer Structured Clinical Interview for DSM diagnoses. A sample of the MINI can be found in [Appendix D](#).

8.3.16.1.3. Seventeen-Item Hamilton Rating Scale for Depression

The HAM-D is a clinician-administered 17-item depression scale designed to be sensitive to treatment effects [[Hamilton 1960](#)]. The Structured Interview Guide for the HAM-D (SIGH-D) will be used for administration. A sample of the SIGH-D can be found in [Appendix E](#).

8.3.16.1.4. Clinical Surveillance Team Eligibility Review for New Subjects

The Clinical Surveillance Team (CST) is a division of PPD CNS Clinical Development. The CST eligibility review is an independent evaluation of the eligibility of the subject. Sites enrolling new subjects will complete the CST Pre-Baseline Packet at screening and forward the data to the CST so that review may be completed as soon as possible after screening and before the next study visit. The investigator may use the results of this tool at his or her discretion.

8.3.16.2. Safety Assessments

8.3.16.2.1. Columbia Suicide Severity Rating Scale

The C-SSRS is a clinician-administered instrument that assesses suicidal ideation and behavior [Posner, 2011]. The “Baseline” version of the instrument will be administered to New Subjects at the screening visit. The “Since Last Visit” version will be administered to all participating subjects at all other visits. A sample of the C-SSRS can be found in [Appendix F](#).

8.3.16.2.2. Clinical Opiate Withdrawal Scale

The COWS is an 11-item questionnaire designed to measure an individual’s level of opiate withdrawal [Wesson and Ling 2003]. The COWS should be administered by a medical professional. A sample of the COWS can be found in [Appendix G](#).

8.3.16.3. Efficacy Assessments

8.3.16.3.1. Montgomery-Åsberg Depression Rating Scale

The MADRS is a clinician-administered, 10-item depression scale designed to be sensitive to the effects of antidepressant treatment [Montgomery and Asberg 1979]. The Structured Interview Guide for the MADRS (SIGMA) will be used for administration. A sample of the SIGMA can be found in [Appendix H](#).

8.3.16.3.2. Hamilton Rating Scale for Anxiety

The HAM-A is a clinician-administered 14-item scale developed to measure the severity of anxiety symptoms [Hamilton 1959]. The Structured Interview Guide for the HAM-A (SIGH-A) will be used for administration. A sample of the SIGH-A can be found in [Appendix I](#).

8.3.16.3.3. Clinical Global Impression – Severity

The CGI-S is a clinician-administered scale that measures severity of mental illness [Guy 2000]. The CGI-S asks that the clinician rates the subject relative to their past experience with patients with MDD. A sample of the CGI-S can be found in [Appendix J](#).

8.4. Study Requirements and Restrictions

8.4.1. Contraception and Pregnancy

All male and female subjects must agree to use an acceptable method of contraception for the duration of the study unless they are surgically sterile or post-menopausal (see below). At a minimum subjects must agree to use one of the following. Additional restrictions, if required, will be clarified in the locally approved informed consent form (ICF).

- Double-barrier protection (eg, a condom with spermicide or a diaphragm with spermicide)
- Intrauterine device (IUD)

- Hormonal contraceptives (eg, birth control pills, a vaginal ring, contraceptive patch, contraceptive implant; must be initiated and at a stable dose for at least 30 days prior to screening; see [Section 8.4.2.2](#)).

Subjects who are abstinent are eligible, provided they agree to use an acceptable contraceptive method should they become sexually active.

Subjects who are surgically sterile are exempt from the requirement to use contraception. Women who have undergone a hysterectomy, bilateral tubal ligation, or bilateral salpingo-oophorectomy are considered surgically sterile. Men who have undergone a vasectomy are considered surgically sterile. Partner vasectomy is not considered an approved acceptable method of contraception for a female subject.

Women who are postmenopausal are also exempt from the requirement to use contraception. For the purpose of this study, postmenopausal is defined as the permanent cessation of menstruation for at least 12 months prior to screening in women who are 45 years of age or older.

If any female subject becomes or is found to be pregnant while participating in the study, she will be discontinued immediately. The investigator must fill out a Pregnancy Report Form and submit the information to the sponsor within 24 hours of awareness of the pregnancy, irrespective of whether an adverse event has occurred. The end-of-treatment and safety follow-up visits will be scheduled.

The investigator will follow the pregnancy until completion or until pregnancy termination and notify the outcome to the sponsor. If the outcome of the pregnancy meets the criteria for immediate classification as a SAE, the investigator should follow the procedure of reporting SAEs (See [Section 13.2](#)).

8.4.2. Concomitant and Prohibited Medications

8.4.2.1. Concomitant Medications

All medications taken by a given subject within 30 days of screening through follow-up will be recorded as detailed in [Section 8.3.10](#). The concomitant medication review on each visit will include all prescription medications including ADT, OTC medications, and vitamins and dietary supplements. Concomitant medications will be reviewed at all clinic visits and all phone assessments.

Subjects will be permitted to continue taking concomitant medications during the study provided that these medications are not prohibited (see [Sections 7.2](#) and [8.4.2.2](#)). The investigator may discontinue or adjust the dose of any of these concomitant medications to ensure subject safety. At the investigator's discretion, new concomitant medications may be administered during the course of the study for the treatment of an AE or a change in disease state. If a prohibited medication is needed, the investigator should notify the medical monitor as soon as possible to discuss the continued participation of the subject in the study.

Dose adjustment of approved ADT during the treatment period is permitted for optimal therapeutic effect within the recommended dose range, however ADT dose adjustment should not be made within the same week as ALKS 5461 dose adjustment. Further, subjects are not permitted to change ADTs during the course of the study period.

See [Section 9.5](#) for complete details of ALKS 5461 dose adjustments.

8.4.2.2. Prohibited Medications

The use of any kind of adjunctive therapy, other than ALKS 5461, at an adequate dose and duration in combination with an ADT at any time during the current MDE for the purpose of augmenting the effects of the ADT is prohibited. Adjunctive therapy other than ALKS 5461 is prohibited from screening through the final follow-up visit. Prohibited adjunctive therapies include, but are not restricted to the following:

- atypical antipsychotics (eg, aripiprazole, quetiapine, olanzapine)
- monoamine oxidase inhibitors (eg, phenelzine, tranylcypromine, selegiline)
- lithium
- tricyclic antidepressants (eg, amitriptyline, nortriptyline, desipramine)
- psychostimulants (eg, methylphenidate, dextroamphetamine/ amphetamine)
- bupropion
- BUP

The use of opioid agonists (eg, codeine, oxycodone, tramadol, morphine) or opioid antagonists (eg, naloxone, naltrexone) within 14 days before screening through the final follow-up visit is prohibited. Use of extended-release opioid antagonists within 2 months prior to screening through the final follow-up visit is prohibited.

The initiation or dose adjustment of hormone replacement therapy (including testosterone) or an oral contraceptive within 30 days of screening is prohibited. Such therapy is permissible if a stable dose of hormone replacement therapy or oral contraceptive is taken for at least 30 days prior to screening and the same stable dose is expected to be taken throughout the study.

Hypnotic agents for insomnia (eg, benzodiazepines, zolpidem, trazodone) are not permitted if started within 30 days of screening or if started at any time during the study. Such agents are permitted if they have been used stably for at least 30 days before screening not more than 3 times/week, and are expected to be used stably at ≤ 3 times/week throughout the study. For an insomnia indication, benzodiazepine is permissible if equivalent to ≤ 2 mg/day of lorazepam, trazodone up to 100 mg/day, zolpidem or zaleplon up to 10 mg/day, or Ambien CR up to 12.5 mg/day. Hypnotic agents are not permitted within 30 days prior to screening through the final follow-up visit if prescribed for an indication other than insomnia.

Use of inducers or moderate to strong inhibitors of CYP3A4 (prescription medications, OTC medications, or dietary supplements) within 30 days before screening through the final follow-up visit is prohibited. See [Appendix A](#) for a list of prohibited inducers and moderate to strong inhibitors of CYP3A4.

8.4.3. Pain Management

Because the ALKS 5461 co-formulation contains samidorphan, a μ -opioid receptor antagonist, patients may experience reduced or ineffective analgesia when taking an opioid analgesic agent concurrently with ALKS 5461, including several days after last dosing of ALKS 5461.

In the event of an emergency, pain management of the subject should include the following:

- Regional analgesia or use of non-opioid analgesics
- If opiate anesthesia or analgesia is required, the subject should be continuously monitored in an anesthesia care setting, by persons not involved in the conduct of the surgical or diagnostic procedure. The opioid therapy must be provided by individuals specifically trained in the use of anesthetic drugs and the management of the respiratory effects of potent opioids, specifically the establishment and the maintenance of a patent airway and assisted ventilation
- Close monitoring by appropriately trained personnel in a setting equipped and staffed for cardiopulmonary resuscitation

For subjects requiring emergency opioid analgesics prior to dosing, the study drug should not be administered. If opioid analgesics are required after the study drug has been dosed, it may take several days for opiate sensitivity to be restored, since samidorphan is an opioid antagonist and could interfere with opioid-mediated pain management.

9. TREATMENT OF SUBJECTS

9.1. Study Drug Dose and Administration

9.1.1. Description of ALKS 5461

The ALKS 5461 drug product will be formulated as tablets for sublingual (SL) administration and will contain a ratio of 1:1 BUP: samidorphan as free base equivalents by weight. BUP is a Schedule III narcotic and samidorphan is a Schedule II controlled substance. Thus, ALKS 5461 should be treated as a Schedule II controlled substance in the US. Outside the US, ALKS 5461 should be handled according to local regulations. See [Section 10](#) for information on storage and handling of controlled substances.

The study drug formulation contains common pharmaceutical excipients that are listed in the US as “GRAS” (Generally Recognized As Safe [GRAS]) and accepted for use as food additives in Europe: lactose monohydrate, microcrystalline cellulose, croscopvidone, sucralose, citric acid, sodium citrate, and magnesium stearate.

9.1.2. Study Drug Dose and Dosing Regimen

Dosing begins at Visit 2, with a 1-week titration for subjects not already taking ALKS 5461 upon study entry. The 1-week titration will be blinded for Continuing Subjects entering from ALK5461-206 and ALK5461-207. See [Section 8.1](#) and [Table 1](#) for details on Week 1 titration and blinding.

One tablet will be taken sublingually on each dosing day. The tablet should be placed under the tongue and kept under the tongue until completely dissolved. **The tablet must not be swallowed.** Eating and drinking should be avoided for 15 minutes after dosing. At Visit 2, study site personnel will administer the tablet and visually confirm that the tablet has dissolved completely. From Day 2 on, subjects will self-administer the daily SL dose; it is recommended that subjects take ALKS 5461 at bedtime.

9.2. Treatment Adherence

According to the schedule in [Table 2](#) and [Table 3](#), at each specified dispensing visit, subjects will receive a supply of ALKS 5461 to last until the following visit. Subjects will be instructed to bring the bottle or blister pack (as applicable, see [Section 10.1](#)) with them to each subsequent visit. Subjects will also be instructed to bring in containers of their ADT. Drug adherence will be reviewed with subjects at each visit.

9.3. Method of Assigning Subjects to Treatment

Three different groups of subjects will be enrolled in this study, some of whom will require a 1-week ALKS 5461 titration, as described in [Section 8.1](#). From Day 8 on, all participating subjects will receive ALKS 5461 2/2.

9.4. Blinding

Subjects who are not already taking ALKS 5461 on study entry will begin treatment with a 1-week titration period. As explained in [Section 8.1](#) and [Table 1](#), to maintain the blinded dosing scheme in antecedent studies ALK5461-206 and ALK5461-207, subjects entering from those studies will be blinded to whether or not they will participate in the 1-week titration. Study subjects, investigators, site staff and the sponsor will remain blinded to the treatment assignment in all applicable antecedent studies.

Beginning on Day 8, all participating subjects will receive open-label ALKS 5461 2/2, as tolerability allows.

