Illicit Substances Review ⁿ	X	X	X	X	X	X	X	X	X	X	X	X	X	X
Exploratory Efficacy Assessments														
HAM-A		X ^c			X		X	X		X		X		X
CGI-S		X ^c	X	X	X	X	X	X	X	X	X	X	X	X
MADRS ^o	X	X ^c	X	X	X	X	X	X	X	X	X	X	X	X
Additional Study Procedures														
Dispense Study Drug ^p		X	X	X	X	X	X	X	X	X	X	X	X	X
Study Drug Adherence Review ^q			X	X	X	X	X	X	X	X	X	X	X	X
ADT Adherence Review ^r		X	X	X	X	X	X	X	X	X	X	X	X	X
Blood sample – PK ^s			X	X	X	X	X	X	X	X	X	X	X	X
Emergency Treatment Card ^t		X	X	X	X	X	X	X	X	X	X	X	X	X

ADT=antidepressant therapy; ATRQ=Massachusetts General Hospital Antidepressant Treatment Questionnaire; CGI-S=Clinical Global Improvement – Severity; COWS=clinical opiate withdrawal scale; C-SSRS=Columbia Suicide Severity Rating Scale; ECG=electrocardiogram; ET=early termination; HAM-A=Hamilton Rating Scale for Anxiety; HAM-D=17-item Hamilton Rating Scale for Depression; MADRS=Montgomery-Åsberg Depression Rating Scale; MINI=Mini International Neuropsychiatric Interview; PK=pharmacokinetic.

- ^a Only New Subjects will participate in the screening visit. Screening may be repeated in some cases for Potential New Subjects, but only after approval by the medical monitor
- ^b Visit 14/ET should occur within 24 hours of the subject's last dose of ALKS 5461
- ^c For Continuing Subjects and Lead-in Subjects, identical assessments taken at the subject's Visit 2 of the antecedent study for Lead in Subjects and last treatment visit of the antecedent study for continuing subjects do not need to be repeated at Visit 2 unless more than 10 days elapses between these visits. If more than 10 days elapses between visits, all assessments must be performed at Visit 2 (ie data cannot be carried forward).
- ^d Eligible, consenting New Subjects will give written consent at the screening visit. Eligible, consenting Continuing Subjects and Lead-in Subjects will give written consent prior to participating in any study-specific procedures on Visit 2
- ^e To be conducted predose on Visit 2
- ^f For hepatitis B surface antigen, anti-hepatitis C antibodies, and human immunodeficiency virus
- ^g Breath alcohol test may be repeated for any participating subject at any point during the study based on investigator's judgment
- ^h Vital sign measurements include oral temperature, respiratory rate, blood pressure, and heart rate. Blood pressure, respiratory rate, and heart rate will be measured after the subject has been in a supine position for at least 5 minutes

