- ⁱ Centralized drug screen testing at screening, local drug screen testing (via dipstick) for all other time points. The urine drug screen at Visit 1 may be repeated based on investigator judgment. The test can also be repeated at any time during the study, should the investigator feel it is warranted
- ^j Serum pregnancy testing at screening; urine pregnancy testing at all other visits
- ^k At screening the "Baseline" version of the C-SSRS will be administered and at all other visits the "Since Last Visit" version will be administered
- ^l COWS to be administered by a medical professional
- ^m All medications (prescription and non-prescription, including vitamins and herbal supplements) including ADT taken within 30 days will be recorded at screening. Any changes will be recorded at subsequent visits
- ⁿ Subject will be queried at screening on illicit substances used within 30 days, with updates made at each subsequent visit
Note: additional dispensation visits may be required based on country specific regulatory requirements. No other activities or assessments are done on these days.
- ^o The MADRS should be administered prior to the HAM-D, CGI-S and HAM-A on visits when multiple assessments are scheduled
- ^p First dose of ALKS 5461 (at Visit 2) to be administered on-site; ALKS 5461 to be dispensed at each indicated visit for subjects to self-administer starting on Day 2. Self-administration should be recommended to occur at bedtime
- ^q Via pill count and subject query
- ^r Via subject query
- ^s One PK blood sample will be collected during each indicated visit from consenting subjects enrolled in the United States only. When PK and safety blood samples are scheduled to be collected on the same day, efforts should be made to collect both samples during the same draw.
- ^t Dispense card on Visit 2; confirm possession of card at each subsequent visit and re-dispense if necessary

Table 3: Schedule of Assessments, Safety Follow-up Period

Evaluation	Safety Follow-up Period										
	1 (+1)	2 (+1)	3 (+1)	4 (+1)	5 (+1)	6 (+1)	7 (+1)	10 (+2)	14 (±2)	21 (+2)	28 (±2)
Days post end of treatment:	366	367	368	369	370	371	372	375 (+2)	379 (±2)	386 (+2)	393 (±2)
Study Day:	366	367	368	369	370	371	372	375 (+2)	379 (±2)	386 (+2)	393 (±2)
Visit ^a	15	Phone	Phone	Phone	Phone	Phone	16	Phone	17	Phone	18
Adverse Event Monitoring ^b	X	X	X	X	X	X	X	X	X	X	X
Concomitant Med Review ^c	X	X	X	X	X	X	X	X	X	X	X
Illicit Substances Review ^c	X						X		X		X

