8.3.15.3. Urine Drug Screening

New Subjects will undergo urine drug screening for drugs of abuse at Visit 1 and laboratory analysis will be centralized. At all other time points specified in [Table 2](#) and [Table 3](#), all participating study subjects will have urine drug screening via dipstick; results will be analyzed by the local laboratory.

Drug screening will be performed for amphetamines, barbiturates, benzodiazepines, cocaine (metabolite), tetrahydrocannabinol, opioids, and phencyclidine. The opioid panel to be performed at screening for New Subjects (analyzed centrally) will include BUP, codeine, hydrocodone, hydromorphone, methadone, morphine, oxycodone, and oxymorphone. Drug screens administered at all other visits as specified in [Table 2](#) and [Table 3](#) (analyzed locally) will include all aforementioned opioids.

Negative urine drug screening at Visit 1 and Visit 2 will be required for a subject to enter in the study. However, an exception may be made for a benzodiazepine, when such medication is medically indicated for insomnia.

The urine drug test at screening may be repeated based on investigator judgment. The test can also be repeated at any time during the study, should the investigator feel it is warranted. Action taken in response to a positive urine drug screen after Visit 2 should be based on a medical evaluation in consultation with the medical monitor.

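### The local Visit 2 dipstick panel includes buprenorphine with no masking rule, so for entrants from ALK5461-206 and -207 it can reveal prior active treatment versus placebo, against Protocol Section 9.4

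*Protocol*

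**What the plan says.** Protocol Section 9.4 explains that Week 1 is blinded for entrants from ALK5461-206 and -207 to preserve those studies' dosing blind, and adds that "Study subjects, investigators, site staff and the sponsor will remain blinded to the treatment assignment in all applicable antecedent studies". Table 1 (Section 8.1) accordingly lists blinded Week 1 dosing for entrants from those two studies, whether they arrive on placebo, on 1/1 (-207 only) or on 2/2.

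Section 8.3.15.3 sets out the urine drug screen. The opioid panel for New Subjects at screening is "analyzed centrally) will include BUP, codeine, hydrocodone, hydromorphone, methadone, morphine, oxycodone, and oxymorphone". For the other scheduled visits the panel is "analyzed locally) will include all aforementioned opioids". As to who is tested and where, "all participating study subjects will have urine drug screening via dipstick; results will be analyzed by the local laboratory". Table 2 footnote i agrees: "local drug screen testing (via dipstick) for all other time points". Table 2 schedules a drug screen at Visit 2 and marks it with footnote e, "To be conducted predose on Visit 2".

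The result bears on entry: "Negative urine drug screening at Visit 1 and Visit 2 will be required for a subject to enter in the study". Exclusion criterion 2 (Section 7.2.1, all subjects) says the same in substance. Both allow an exception only for a benzodiazepine taken for insomnia.

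**The concern.** BUP is half of the study drug. A predose BUP result at Visit 2 reflects what the subject took before entering this study, and for an entrant from -206 or -207 that is the assignment Section 9.4 says stays hidden. The blinded Week 1 pack protects the assignment from that point on, but the screen comes before it.

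Two things are at stake. First, Lead-in Subjects enter within 10 days of completing the prospective lead-in of -205, -206 or -207 (Section 7.1.4). This indicates that enrolment here overlaps with at least some of those studies. If sites learn the assignments of subjects who have rolled over, they may also learn which side-effect pattern goes with active drug while others are still being rated. Second, SAP Section 3.1 summarises safety and efficacy by prior ALKS 5461 exposure. For -206 and -207 entrants, the strip can disclose that grouping to the people reporting adverse events and rating outcomes.

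**Working it through.** The plan gives no figure to reproduce. The check is a cross-reading, followed by an illustration on assumed inputs.

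**Cross-reading**

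1. *Is BUP on the Visit 2 strip?* Yes as written. Section 8.3.15.3 carries all the listed opioids over to the local tests, and no exception is made for subjects coming from ALKS 5461.
2. *Is the test before the first dose here?* Yes, by Table 2 footnote e. Table 1 gives every entrant some ALKS 5461 from Day 1, so the predose result is the one that discriminates.
3. *Must someone involved in entry know the result?* Yes. A negative screen is an entry condition, so the result has to reach whoever confirms eligibility.
4. *Is the BUP result masked or sent to an unblinded party?* No such rule appears in Sections 7.2.1, 8.3.15.3 or 9.4 or in the Table 2 footnotes. SAP Section 3.7.4.2 says drug screening data will be listed and does not mention masking.
5. *Does the carry-forward waiver remove the problem?* Section 8.1, Section 8.3.2 and Table 2 footnote c let Continuing Subjects rely on identical assessments from the last antecedent treatment visit if no more than 10 days have passed. Inclusion criterion 13 puts every Continuing Subject inside that window. There are two cases:
   - The antecedent visit had no screen, or one without BUP. It is then not identical, and the Visit 2 strip is due.
   - The antecedent screen was identical, so it included BUP. The carried-forward result is then just as revealing and is still needed for eligibility.

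   Neither case protects the blind. The protocol does not say which applies.
6. *Which entrants?* Those from -206 and -207. Table 1 gives -205 entrants (after a 1-week discontinuation) and -210 entrants unblinded Week 1 dosing.

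**How informative is a result?**

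The documents give neither the strip's accuracy for BUP nor the share of -206 and -207 entrants who had active drug. Assumptions: active share *p* from 1/3 to 2/3, sensitivity *Se* 50–99%, specificity *Sp* 95–99%.

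- P(active | positive) = *p·Se* / [*p·Se* + (1−*p*)(1−*Sp*)]
- P(placebo | negative) = (1−*p*)*Sp* / [(1−*p*)*Sp* + *p*(1−*Se*)]

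| | Inputs (*p*, *Se*, *Sp*) | Calculation | Result |
|---|---|---|---|
| Positive, low | 1/3, 0.50, 0.95 | 0.1667 / (0.1667 + 0.0333) | 0.833 |
| Positive, high | 2/3, 0.99, 0.99 | 0.6600 / (0.6600 + 0.0033) | 0.995 |
| Negative, low | 2/3, 0.50, 0.95 | 0.3167 / (0.3167 + 0.3333) | 0.487 |
| Negative, high | 1/3, 0.99, 0.99 | 0.6600 / (0.6600 + 0.0033) | 0.995 |

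If sensitivity is only 30%, for example because several days have passed since the last dose, a positive still means active with probability 0.75 to 0.98. A negative then means placebo with probability only 0.40 to 0.74.

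Without the strip, the chance of active is *p* itself, 1/3 to 2/3. A positive therefore adds a great deal across the whole range; a negative does so only if sensitivity is high.

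**The case against.** The strongest objection is the carry-forward waiver. Section 8.3.2 goes further than Section 8.1 and says identical assessments will not be repeated within the 10-day window. If the antecedent final visit had an identical screen, few or no Visit 2 strips would be run in these entrants. This stands as a limit on how many subjects have a strip, and the antecedent protocols are not available to settle it. It does not restore the blind, for the reasons under step 5, and the investigator may repeat the test at any time.

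Other limits also stand:

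- A reader might infer that site staff read the strip. The text says the local laboratory analyses it. What follows from the documents is only that someone confirming eligibility must learn the result.
- A reader might infer that nearly every assignment can be read off, with a negative strip proving placebo. No cutoff, sensitivity or detection window is given, and the gap since the last dose may reach 10 days.
- A reader might infer that full -207 assignments are exposed. A positive or negative result cannot separate 1/1 from 2/2.
- A reader might extend the point to -205. Those entrants have unblinded Week 1 dosing, and Section 9.4 names only -206 and -207 as the schemes being preserved.
- No result of this study is shown to be biased. It has no reference therapy, is open-label from Day 8 and is summarised descriptively. Any effect on -206 or -207 depends on their timing and rating arrangements, which are not described here.

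**Conclusion.** The point holds in a conditional form. As written, Section 8.3.15.3 and the Visit 2 entry rule make available a result that can separate active from placebo for -206 and -207 entrants, and nothing in the protocol keeps it from those whom Section 9.4 says stay blinded. It applies where the Visit 2 screen is performed or an identical BUP-containing screen is carried forward; the number of such subjects cannot be derived from the documents. Under the assumptions above, a positive is strongly informative throughout, while a negative ranges from close to uninformative to nearly conclusive. The stronger reading, that the screen unmasks all Continuing Subjects, is not supported.

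The eligibility conflict is related but distinct. Read literally, criterion 2 and Section 8.3.15.3 bar a BUP-positive entrant, although Table 1 plans for subjects already on ALKS 5461. Exempting BUP from the entry rule would settle entry but leave the result in view.

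**What to change.** - In Section 8.3.15.3 and Table 2 footnote i, specify a local Visit 2 panel without BUP for Continuing Subjects from -206 and -207.
- Apply the same rule to any carried-forward screen (Table 2 footnote c, Sections 8.1 and 8.3.2) and to repeat tests before Day 8.
- Withhold any BUP result already on file from site and sponsor study staff until the antecedent study is unblinded.
- Cross-refer to these rules in Section 9.4.
- Reconcile the negative-screen sentence in Section 8.3.15.3 and exclusion criterion 2 with Table 1. Without this, withholding a BUP result would leave the entry condition impossible to confirm. For that reason a masked central BUP test alone would not be enough.

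The cost is a different strip at one visit for one group of entrants, and a short amendment. The downside is that non-study BUP use by placebo entrants would not be seen at Visit 2.
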